	safety of NOCDURNA using longitudinal real-world data. In addition, since it is desirable to put these observations into context and characterise a population with similar indications who do not receive desmopressin, a similar number of patients receiving standard care for other lower urinary tract symptoms (LUTS) will be evaluated in order to inform on the safety and utilisation of NOCDURNA	
	 Primary objective: To estimate the incidence rate of symptomatic hyponatraemia (defined as a recorded diagnosis of hyponatraemia) among patients treated with NOCDURNA, and patients with LUTS separately, overall and by subgroups of interest (including elderly patients, aged ≥65 years). 	
	Secondary objectives:	
	 To describe demographic and health characteristics of the population receiving NOCDURNA and patients with LUTS, including prevalence of risk factors for outcomes of interest. 	

.

	 To estimate incidence rate of hyponatraemia requiring hospital intensive care among patients treated with NOCDURNA and patients with LUTS separately.
	 To estimate incidence rate of clinically significant hyponatraemia (defined as a serum sodium concentration of <130 mmol/L) among patients treated with NOCDURNA and patients with LUTS separately.
	 To estimate rate of all-cause mortality among patients treated with NOCDURNA and patients with LUTS separately.
	 To estimate incidence rate of the following events of special interest among patients treated with NOCDURNA and patients with LUTS separately: Major cardiovascular events (MACE, composite endpoint) Major venous thromboembolic events (VTE, composite endpoint)
	To estimate incidence rate of acute exacerbation of congestive heart failure among patients who have chronic cardiac insufficiency treated with NOCDURNA, and patients with LUTS, separately.
	6. To estimate incidence rate of primary and secondary outcomes of interest between patients treated with NOCDURNA compared to a population of LUTS patients adjusted for confounding factors, by country where data available.
	 To estimate incidence rate of cardiovascular and thromboembolic events of interest resulting in treatment withdrawal of NOCDURNA
	8. To estimate incidence rate in patients adhering to the label as assessed by the proxy based on diagnosis and contra- indication (as available)
	All secondary objectives will be evaluated in the overall population and among subgroups of interest (including elderly, aged ≥65 years).
Countries of study	Denmark, Germany and Sweden

2 LIST OF ABBREVIATIONS

Abbreviation	Definition	
ATC	Anatomic Therapeutic Chemical	
BIPS	The Leibniz Institute for Prevention Research and Epidemiology	
CI	Confidence interval	
CPR	Central Person Registry	
DA	Disease Analyzer	
DCP	Decentralised procedure	
DCRS	Danish Civil Registration System	
DNPR	Danish National Patient Registry	
DRCD	Danish Registry of Causes of Death	
DRMPS	Danish Registry of Medicinal Products Statistics	
EMA	European Medicines Agency	
ENCePP	European Network of Centres for Pharmacoepidemiology and Pharmacovigilance	
EU	European Union	
EU PAS Register	European Union electronic Register of Post-Authorisation Studies	
GEP	Good Epidemiological Practice	
GePaRD	The German Pharmacoepidemiological Research Database	
GPP	Good Pharmacoepidemiology Practice	
GPS	Good Practice of Secondary Data Analysis	
GVP	Good pharmacovigilance practices	
ICD-10	International Classification of Diseases, 10 th Revision	
IRR	Incidence rate ratio	
ISPE	International Society of Pharmacoepidemiology	
LPD	Longitudinal population database	
LUTS	Lower urinary tract symptoms	
MACE	Major adverse cardiovascular events	
MPA	Medical Products Agency	
NBHW	National Board of Health and Welfare	
PASS	Post-authorization safety study	
PIN	Personal identity number	
SAP	Statistical analysis plan	
SCDR	Swedish Cause of Death Registry	
SHI	Statutory Health Insurance	
SIR	Swedish Intensive Care Registry	
SmPC	Summary of product characteristics	
SNPR	Swedish National Patient Registry	
SPDR	Swedish Prescribed Drug Registry	
STPR	Swedish Total Population Registry	
STROBE	Strengthening the reporting of observational studies in epidemiology	
THIN	The Health Improvement Network	
VTE	Venous thromboembolism	

3 **RESPONSIBLE PARTIES**

Sponsor:

Ferring Pharmaceuticals A/S, [name], [name], Denmark.

Subcontractor acting as contracted principal investigator:

(To be confirmed)

4 ABSTRACT

Title

Post-authorisation safety study of NOCDURNA for the symptomatic treatment of nocturia due to idiopathic nocturnal polyuria: A multi-country cohort study using secondary data.

Rationale and background

Nocturia is defined as a complaint that an individual has to wake at night one or more times to void where each micturition is preceded and followed by sleep. Nocturia can be due to many factors, such as an underlying medical condition. However, some people experience nocturia due to idiopathic nocturnal polyuria, which means that although their total 24-hour production may remain normal, they produce an excessive amount of urine at night.

In 2016, Ferring Pharmaceuticals A/S, hereafter referred to as Ferring, finalised a decentralised procedure (DCP) in the European Union (EU) leading to the approval of NOCDURNA (desmopressin, gender-specific low doses of 25 µg for women and 50 µg for men) for the symptomatic treatment of nocturia due to idiopathic nocturnal polyuria in adults. Some safety concerns relating to NOCDURNA were defined during the EU DCP; risk of hyponatraemia (especially in elderly patients aged ≥65 years), a potential risk of thromboembolic events (only expected at doses much higher than approved for NOCDURNA), and a potential risk of acute exacerbation of congestive heart failure in patients with compensated cardiac insufficiency. These safety concerns were based on data from clinical trials in haemophilia (OCTOSTIM, high-dose trials, exposure in the magnitude 10-20 higher than for urological indications), post-marketing experience and general knowledge about pharmacodynamics and physiology.

Against this background, the DCP member states have required that a post-authorisation safety study (PASS) is included in the NOCDURNA risk management plan to evaluate safety concerns and to collect long-term data on patients aged ≥65 years treated with NOCDURNA according to the approved summary of product characteristics.

Research question and objectives

Primary objective:

To estimate the incidence rate of symptomatic hyponatraemia (defined as a recorded diagnosis of hyponatraemia) among patients treated with NOCDURNA, and patients with lower urinary tract symptoms (LUTS) separately, overall and by subgroups of interest (including elderly patients, aged \geq 65 years).

Secondary objectives:

The secondary objectives are to:

- 1. Describe the demographic and health characteristics of the population receiving NOCDURNA and patients with LUTS, including prevalence of risk factors for outcomes of interest.
- 2. Estimate the incidence rate of hyponatraemia requiring hospital intensive care among patients treated with NOCDURNA and patients with LUTS separately.
- Estimate the incidence rate of clinically significant hyponatraemia (defined as a serum sodium concentration of <130 mmol/L) among patients treated with NOCDURNA and patients with LUTS separately.
- 4. Estimate the rate of all-cause mortality among patients treated with NOCDURNA and patients with LUTS separately.
- 5. Estimate the incidence rate of the following events of special interest among patients treated with NOCDURNA and patients with LUTS separately:
 - a. Major adverse cardiovascular events (MACE, composite endpoint)
 - b. Major venous thromboembolic events (VTE, composite endpoint)

Estimate the incidence rate of acute exacerbation of congestive heart failure among patients who have chronic cardiac insufficiency treated with NOCDURNA, and patients with LUTS, separately. In addition, a subgroup analysis of all patients adhering to the label as assessed by the proxy based on diagnosis and contra-indications (as available) will be conducted.

- 6. Estimate the incidence rate of primary and secondary outcomes of interest between patients treated with NOCDURNA compared to a population of LUTS patients adjusted for confounding factors, by country where data available.
- 7. Estimate the incidence rate of cardiovascular and thromboembolic events of interest resulting in treatment withdrawal of NOCDURNA.

All secondary objectives will be evaluated in the overall population and among subgroups of interest (including elderly, aged \geq 65 years).

Study design

Multi-country, cohort study using secondary data collected from research databases and administrative national healthcare registries in selected European countries: Denmark, Germany and Sweden. These countries have been selected following careful consideration of multiple factors: a feasibility assessment of the ability of candidate data sources to address the study objectives, recommendations by the Swedish Medical Products Agency (MPA) and expected uptake of NOCDURNA in candidate countries of study.

Cohorts of patients with newly initiated treatment of NOCDURNA or with newly initiated treatment for LUTS will be identified from existing data sources in each country of study. If sample size permits, comparative analyses of incidence rate will be conducted for the primary and secondary outcomes of interest. The comparator group will be patients with LUTS. The incidence rate ratio (IRR) will be adjusted for by relevant confounding factors, such as age and gender (to be detailed in the statistical analysis plan (SAP)).

The study period will be between the launch of NOCDURNA and latest data availability in each country, considering that the final study report is planned for 2023. For each of the countries, the planned study periods are as follows: Denmark – 29 August 2016 to 31 December 2021; Germany – 1 January 2017 to 31 December 2021; and Sweden – 20 January 2017 to 31 December 2021. The difference in start of the study period across countries is dictated by the difference in NOCDURNA launch dates.

The index date for NOCDURNA patients is the dispensation date of the first dispensed prescription for NOCDURNA during the study period. For LUTS patients, the index is the date of first dispensed LUTS-defining drug in the study period.

Population

The cohort of NOCDURNA patients will consist of individuals meeting the following *inclusion criteria:*

- A first-ever dispensed prescription for NOCDURNA [desmopressin; Anatomical Therapeutic Chemical (ATC) code: H01BA02; brand name: NOCDURNA; dose: 25 or 50 microgram] recorded in the relevant country-specific data source between its launch date and the latest date of data availability in each country
- Aged 18 years and above on index date
- At least 12 months' registration in the relevant country-specific database(s) prior to the index date, to ensure a sufficiently long period of baseline data availability

Exclusion criteria:

The following exclusion criteria will be applied to the NOCDURNA cohort:

- Treatment with vasopressin or any of its analogues (defined as a dispensed prescription within 6 months before the index date; ATC codes H01BA), irrespective of formulation or dose/strength
- Multiple desmopressin drugs dispensed on the index date

The LUTS cohort will consist of individuals meeting the following inclusion criteria:

- At least one dispensed prescription for a medication used to treat urinary frequency and incontinence (ATC codes G04BD) or benign prostatic hypertrophy (ATC codes G04C) between the launch date of NOCDURNA and the latest date of data availability in each country.
- Aged 18 years and above at index date

Exclusion criteria:

The following *exclusion criterion* will be applied to the LUTS cohort:

• Treatment with vasopressin or any of its analogues (defined as a dispensed prescription within 6 months before the index date; ATC codes H01BA), irrespective of formulation or dose/strength

Subpopulations of interest:

Elderly patients (≥65 years of age at index) will be considered a subpopulation of special interest, for which separate analyses will be performed.

Furthermore, the following patient groups will be considered as subpopulations of special interest, as they are contraindications for NOCDURNA use. Numbers permitting, sub-analyses will be performed according to the NOCDURNA and the LUTS group overall and by the elderly.

- For the primary outcome:
 - History of hyponatraemia
 - o Polydipsia
 - Concomitant use of loop diuretics
 - Concomitant use of glucocorticoids
 - Congestive heart failure (chronic)
 - Kidney disease (chronic kidney disease stage 3 and over)
 - Syndrome of inappropriate antidiuretic hormone secretion (SIADH)
- Additionally, for the cardiovascular disease outcome: uncontrolled hypertension
- Additionally, for the thromboembolic event outcome: coagulation disorders

Variables

Exposure (based on dispensed prescriptions):

Exposure person-time will be defined for NOCDURNA patients from the date of first NOCDURNA prescription. For comparative analyses, equivalent person-time in the LUTS contextual cohort group will be defined from the index date.

Outcomes:

- Primary outcome:
 - Symptomatic hyponatraemia, as defined by a primary or secondary diagnosis of hyponatraemia (International Classification of Diseases, 10th Revision (ICD-10) code: E87.1) (In Germany: discharge diagnosis)
- Secondary outcomes
 - Hyponatraemia requiring hospital intensive care, defined as a primary or secondary diagnosis of hyponatraemia (ICD-10: E87.1) recorded in an intensive care unit
 - Clinically significant hyponatraemia, defined as a serum sodium concentration of <130 mmol/L. Hyponatraemia by level of severity (mild, moderate, severe) will be evaluated as part of this outcome.
 - All-cause mortality
 - Major adverse cardiovascular events (MACE), defined as a record of myocardial infarction and stroke. Fatal and non-fatal events will be considered separately.
 - Major venous thromboembolic events, defined as a record of a deep vein thrombosis, pulmonary embolism or portal vein thrombosis. Fatal and nonfatal events will be considered separately.
 - Acute exacerbation of congestive heart failure
 - MACE and VTE events resulting in treatment withdrawal of NOCDURNA

Covariates (assessed at the index date to the extent available in each data source):

- Demographics
- Treatment indication
- Comorbidities
- Co-medications
- Sodium concentration (Sweden/Denmark)

Data sources

Secondary data on exposure, outcomes and covariates will be collected from research databases and administrative national healthcare registries in Denmark, Germany and Sweden. In Denmark and Sweden, the national registries will be used. In Germany, the German Pharmacoepidemiological Research Database (GePaRD) based on insurance claims data will be used.

Study size

The primary objective is descriptive. All available patients with a NOCDURNA prescription in the study time period will be included in this study. Based on available sales data, the number of NOCDURNA patients within the study time period is estimated to be at least 2650 for Germany (GePaRD), 2610 for Sweden, and 1830 for Denmark.

Data analysis

The incidence rate of the primary outcome reported since index date in the study observation period will be modelled using a Poisson regression model and expressed as number of cases per 1000 patients-years at risk (+95% confidence interval (CI)) for the NOCDURNA group and the LUTS contextual cohort, separately. The model will be adjusted for relevant strong risk factors for events of interest (gender, age (<65, 65-74, \geq 75 years)), and stratum-specific incidence rates will be examined.

Separate Poisson regression models will be applied to (1) include only the first month after index date, and (2) include only subsequent months (month 2 after index and onwards), because Phase III pivotal clinical trials showed hyponatraemia incidence to be higher in the first month of treatment with NOCDURNA than after this time. For both the NOCDURNA and the LUTS group incidence rates will be estimated with 95% CI.

To investigate how the hazard of hyponatremia more precisely develops in time, hazard functions, based on Cox regression models for time to first event since index date will be plotted as a function of time.

Where possible, for the comparative analyses of primary and secondary outcomes of interest, the same analyses will be applied (Poisson regression) but now with the treatment group (NOCDURNA/LUTS) as a factor. To investigate if IRR depend on confounders, treatment by confounder interactions term will be investigated to see if and to what extent IRR depend on the respective confounding factor.

The same analyses conducted for the primary outcome of interest will also be applied for the secondary outcomes of interest.

Sensitivity analyses on the treatment episode definition will be performed to assess the robustness of the study findings.

The statistical analysis will be conducted using the SAS[®] software (version 9.3 or later) on Windows™ (SAS Institute, North Carolina, US) or using R program (version 3.5.0 or later).

Milestones

Study milestones are:

•	Final study protocol	in Q3, 2020

- Start of data collection in Q1, 2021
- Planned end of data collection in Q2, 2023
- Registration in the EU PAS Register in Q1, 2021
- Interim report(s) of study results in Q4, 2021; Q4, 2022

Post Authorization Safety Study (PASS) Protocol Study Number: 000248

• Final report of study results in Q4, 2023

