9.2.5 Subpopulations of interest

Elderly patients (≥65 years of age at index) will be considered a subpopulation of special interest, for which separate analyses will be performed.

Furthermore, the following patient groups will be considered as subpopulations of special interest, as they are contraindications for NOCDURNA use. Numbers permitting, sub-analyses will be performed according to the NOCDURNA and the LUTS group overall and by the elderly.

For the primary outcome:

- History of hyponatraemia
- Polydipsia
- Concomitant use of loop diuretics
- Concomitant use of glucocorticoids
- Congestive heart failure (chronic)
- Kidney disease (chronic kidney disease stage 3 and over)
- Syndrome of inappropriate antidiuretic hormone secretion (SIADH)

- Additionally, for the cardiovascular disease outcome: uncontrolled hypertension
- Additionally, for the thromboembolic event outcome: coagulation disorders

See Annex 3, Table A2 for diagnostic codes.

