9.9.1 Definition of primary outcome

The ICD-10 diagnosis code (E87.1) used to define the primary outcome of the study, hyponatraemia, encompasses both hypo-osmolality and hyponatraemia, though hyponatraemia is recognised as the most common electrolyte disorder. Therefore, it may be possible that the incidence of hyponatremia is overestimated. On the other hand, the diagnosis code is expected to be underutilised in clinical practice, leading to underestimation of the incidence of hyponatraemia. This underestimation is not expected to differ between the NOCDURNA cohort and the LUTS cohort, although it cannot be ruled out that misclassification of the outcome may be differential. Consequently, the estimation of the IRR of hyponatraemia could be impacted.

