Annex 3 Definitions of the LUTS cohort, outcome events and covariates

Table A1. ATC codes used to define the LUTS cohort

Characteristic	ATC code	Description
Overactive bladder	G04BD	Drugs for urinary frequency and incontinence
Benign prostatic hyperplasia	G04C	Drugs used in benign prostatic hypertrophy

Characteristic	ICD-10	ATC	Description
	code	code	
Hyponatraemia	E87.1		
Polydipsia	R63.1		
Loop diuretics		C03C	
Glucocorticosteroids		H02AB	
Congestive heart failure	150.2		Systolic (congestive) heart failure
	150.3		Diastolic (congestive) heart failure
	150.4		Combined systolic (congestive) and diastolic (congestive) heart failure
Chronic kidney disease	N18.3		Chronic kidney disease, stage 3 (moderate)
	N18.4		Chronic kidney disease, stage 4 (severe)
	N18.5		Chronic kidney disease, stage 5
	N18.6		End stage renal disease
Syndrome of inappropriate antidiuretic hormone secretion	E22.2		
Uncontrolled hypertension	I16		Hypertensive crisis
	167.9		Hypertensive encelopathy
Coagulation disorders	D68.0		Von Willebrand's disease
	D68.5		Primary thrombophilia
	D68.6		Other thrombophilia

Table A2. Codes used to define subpopulations of interest

Outcome	ICD-10 code	Description
Hyponatremia		
Hyponatraemia	E87.1	
Hyponatremia (biochemical definition)	n/a	Will be ascertained using biochemical definition: serum sodium concentration <135 mmol/L (mild hyponatraemia) Evaluated only in Denmark
Major cardiovascular events (MACE)	
Myocardial infarction	121, 122	
Stroke, ischemic	163.3-163.9, 166	
Major venous thromboembolic	c events	
Pulmonary embolism	126	
Deep vein thrombosis	180.1–180.9	
Portal vein thrombosis	181	
Mortality		
All-cause mortality	Any	Death from any cause
Heart failure		
Heart failure	150	

Table A3. Codes used to define outcome events

Table A4. Codes used to define covariates

Covariate	ICD-10 code	ATC code	Description/comment
Comorbidities			
History of hyponatraemia, MACE	Please refer to		
and VTE	Table A1		
Polyuria	R35		Polyuria
Diabetes mellitus	E10		Type 1 diabetes mellitus
	E11		Type 2 diabetes mellitus
	E12		Malnutrition-related diabetes
			mellitus
	E13		Other specified diabetes mellitus
	E14		Unspecified diabetes mellitus
Diabetes insipidus	E23.2		
Overactive bladder	N31.0		Uninhibited neuropathic bladder, not elsewhere classified
	N31.2		Flaccid neuropathic bladder, not elsewhere classified
	N31.9		Neuromuscular dysfunction of bladder, unspecified
	N39.4		Other specified urinary incontinence

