The analysis will first calculate the treatment cessation date and then within a 14 days window before the treatment cessation date examine if there is a MACE or VTE event reported from the intensive care register.

Secondary objective 9: Incidence rate in patients stratified according to the label by proxy

The analysis of this outcome will be performed analogous to that of incident events of symptomatic hyponatraemia but only for the Nocdurna ® patients. The subgroup of patients adhering to the label will be defined by a proxy based on diagnosis and contra-indications as stated in the SmPC and the data for classifying the patients according to contraindications should be done as available in the respective registries.

Two population will be created for all Nocdurna ® patients, one with contra-indication for treatment and another as the remaining Nocdurna ® patients without contra-indication. The contra-indication for treatment must be present before the first recorded dispensation of Nocdurna ®.

The following diseases will be considered as contraindications for the prescription of Nocdurna ®, if the diseases are found before or at the index date.

- History of hyponatraemia
- Polydipsia
- Congestive heart failure (chronic)
- Kidney disease (chronic kidney disease stage 3 and over)
- Syndrome of inappropriate antidiuretic hormone secretion (SIADH)

The ICD 10 codes for the above can be found in the given in Table 71. The analysis will be done by using the SAS macro 'Nocdurna_mac' and changing the macro call with 'compare=Off label' and creating a class group with 'Off label' instead of 'LUTS' as described in section 16.1

The analysis of the sub-population will be done for the primary objective and for secondary objective 2, 3, 4, 5a, 5b and 6.

Observe that this analysis is changed from the description in the study protocol.

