Number of events	229	169	60	58	44	14
Total person years (y)	406.1	268.8	137.3	179.2	113.6	65.6
Mean unadjusted rate of events (events/1000 Person-years)	650.5	720.6	513.7	366.3	415.8	282.7
Variance of unadjusted rate	611.2	610.4	613.6	603.0	619.4	575.3
Number of patients with more than 1 event	13	11	2	4	3	1
Number of events in patients with more than 1 event	26	22	4	8	6	2
Number of patients with at least one event	Xx	Xx	Xx	Xx	Xx	Xx
Incidence rate (95 % CI)	513.14 (465.63 - 565.51)	628.77 (565.80 - 698.74)	421.10 (359.52 - 493.23)	297.85 (249.79 - 355.15)	386.66 (314.79 - 474.93)	207.78 (151.08 - 285.75)
Standard Error of Mean	25.44	33.85	33.97	26.74	40.57	33.78
Scale - one value for each model	0.6639	0.6936	0.6043			
Patients >= 65 years						
Number of subjects	2435	1573	862	1038	650	388
Number of events	379	281	98	100	69	31
Total person years (y)	352.4	230.4	122.0	152.6	96.6	56.0
Mean unadjusted rate of events (events/1000	1332	1519	993	843	915	722
Person-years) Variance of unadjusted rate	648	646	649	646	661	620
Number of patients with more than 1 event	22	19	3	7	4	3
Number of events in patients with more than 1	46	40	6	14	8	6
event Number of patients with at least one event	Xx	Xx	Xx	Xx	Xx	Xx
Incidence rate (95 % CI)	994.08 (912.02 - 1083.53)	1225.03 (1115.13 - 1345.76)	801.29 (695.41 - 923.29)	616.35 (527.97 - 719.52)	725.40 (600.62 - 876.09)	555.75 (432.23 - 714.58)
Standard Error of Mean	43.70	58.75	57.94	48.67	69.86	71.28
Scale - one value for each model	0.7701	0.7995	0.7140			

SOURCE DOCUMENT: demo_contra.SAS GENERATED: 22:53:48 16JAN2021 DB version DEV: Simulated data, USERID: [name]

Table 39. Secondary objective 9. Incidence of hyponatraemia requiring hospital intensive care for patients with and without contraindications for Nocdurna ® use. Only Nocdurna ® patients in Sweden.

Repeat Table 38 with hyponatraemia requiring hospital intensive care as outcome in hospital intensive care for patients with and without contraindications for Nocdurna ® use. Only Nocdurna ® patients in Sweden.

Table 40. Secondary objective 9. Incidence of clinically significant hyponatraemia for patients with and without contraindications for Nocdurna ® use. Only Nocdurna ® patients in Denmark.

Repeat Table 38 with clinically significant hyponatraemia as outcome for patients with and without contraindications for Nocdurna ® use. Only Nocdurna ® patients in Denmark.

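### In the Danish label-status analysis, history of hyponatraemia is read from E87.1 alone, so an uncoded pre-index sodium <130 mmol/L leaves a patient with no other listed contraindication in the group without contraindication

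*Protocol*

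**What the plan says.** The Abstract and protocol section 9.2.5 introduce the subgroups with the words "the following patient groups will be considered as subpopulations of special interest, as they are contraindications for NOCDURNA use". Section 9.2.5 names history of hyponatraemia first among them and directs the reader to the code list: "See Annex 3, Table A2 for diagnostic codes". In that list ("Table A2. Codes used to define subpopulations of interest") the hyponatraemia row holds E87.1 and no sodium criterion.

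Protocol section 9.7.2.11 splits the NOCDURNA cohort in two: patients with a contraindication before the first dispensation, and all the rest. It leaves the detail of the proxy to the SAP. The SAP text for secondary objective 9 settles it: "The ICD 10 codes for the above can be found in the given in Table 71". SAP Table 71 again gives E87.1 alone. The shell for SAP Table 40 (NOCDURNA patients in Denmark) reads: "Repeat Table 38 with clinically significant hyponatraemia as outcome for patients with and without contraindications for Nocdurna ® use".

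Three other places bear on this:
- Section 9.9.1 says of E87.1 that "the diagnosis code is expected to be underutilised in clinical practice".
- The Abstract and section 9.3.3 list "Sodium concentration (Sweden/Denmark") among the covariates. Section 9.3.3 sets a look-back of at least 12 months before index, to the extent the data are available.
- Section 9.4.1.4 describes a Danish laboratory database covering four regions, with data starting between Q4 2013 and Q3 2015 depending on the region.

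A sodium-based definition appears only in the outcome tables (protocol Table A3, SAP Table 72): "serum sodium concentration <135 mmol/L (mild hyponatraemia"), for Denmark only.

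**The concern.** The label split has no category for unknown status. A history that the code misses is counted as label-adherent use. In Denmark the study links a source that can show such a history directly, but does not use it for this purpose.

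Table 40 makes the mismatch plain. A sodium of 128 mmol/L after index is an event of clinically significant hyponatraemia. The same value before index does not count as a history of hyponatraemia. Protocol section 7 names low baseline sodium as a significant risk factor for hyponatraemia under desmopressin, so these patients can be expected to have a higher rate of later events. They would raise the rate in the group without contraindication. According to section 7, the regulators asked for data on patients treated according to the SmPC, so that group is one the study exists to describe.

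**Working it through.** **1. Definitions side by side**

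| Use | Place | Definition |
|---|---|---|
| Contraindication subgroup and label proxy | Protocol Table A2, SAP Table 71 | E87.1 only |
| Laboratory outcome | Protocol 9.3.2.2, SAP 2.1.2, Table 40 | sodium <130 mmol/L |
| Outcome code table | Protocol Table A3, SAP Table 72 | E87.1; biochemical <135 mmol/L, Denmark only |
| History of hyponatraemia as covariate | Protocol Table A4 | refers to Table A1, which lists the LUTS drug codes |
| Same covariate | SAP Table 73 | refers to Table 72, which includes the biochemical definition |

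No passage applies pre-index sodium to the label proxy.

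**2. Is pre-index sodium available?** The latest region starts in Q3 2015, so by 30 September 2015. The stated Danish study start is 29 August 2016. Even a patient entering on the first day in the latest region has about 11 months of possible laboratory history, and later entrants have more. Against this, section 9.4.1.4 states only outcome ascertainment as the use of the database, and SAP section 6.1.4 marks baseline laboratory parameters as not applicable. Both conflict with the sodium covariate in section 9.3.3.

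**3. Number of Danish patients.** Protocol Table 4: 82,260 lyophilisates / (360 × 0.5) = 457 patients per year. Over 2018-2021, 457 × 4 = 1828, against the stated 1830. The plan's figure reproduces. Laboratory coverage: 4.4 million of 5.7 million residents (sections 9.4.1.4 and 9.4.1.2), so 1830 × 4.4/5.7 = about 1413 patients.

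**4. Size under assumed inputs.** The documents give neither the prevalence of a low pre-index sodium nor the sensitivity of E87.1. Assumed ranges:
- p, the share with a recorded pre-index sodium <130 mmol/L: 1% to 5%
- s, the share of those who carry E87.1: 10% to 50%
- RR, their later event rate relative to the other patients: 2 to 10

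Patients misplaced = 1413 × p × (1 − s). Their share of the E87.1-negative group is f = p(1 − s)/(1 − ps). Overstatement of that group's rate = f(RR − 1), taking the share of person-time as equal to the share of patients.

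| p | s | RR | Misplaced | f | Overstatement |
|---|---|---|---|---|---|
| 1% | 50% | 2 | 7 | 0.005/0.995 = 0.5% | 0.5% |
| 3% | 30% | 5 | 30 | 0.021/0.991 = 2.1% | 8.5% |
| 5% | 10% | 10 | 64 | 0.045/0.995 = 4.5% | 41% |

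The formula treats every E87.1-negative patient as without contraindication. Some are already flagged for heart failure, chronic kidney disease stage 3 or above, polydipsia or SIADH, so these counts run high.

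**The case against.** **The definition can be defended as deliberate.** Section 9.2.5 lists history of hyponatraemia under the primary outcome, which is itself E87.1, and the same code serves all three countries. Section 9.7.2.11 calls the measure a proxy based on diagnosis. This stands for the primary outcome and for pooled results, and is the reason to keep the code-only version there. It does not help Table 40, whose outcome is a sodium value.

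**The protocol leaves the proxy open.** True of section 9.7.2.11, which refers to what the registries hold and defers to the SAP. The SAP then points to ICD-10 codes only.

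**Laboratory history exists only for tested patients.** This stands. SAP section 10.2.3 itself raises differences in the likelihood and intensity of testing. A laboratory criterion makes label status depend partly on earlier testing, so the number tested must be reported.

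**Underuse of the code is already a stated limitation.** Section 9.9.1 discusses it for the outcome, not for the history. Section 9.9.4 mentions incomplete recording of diagnoses only in general terms.

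**Stronger readings the documents do not support.**
- A reader might infer that every Danish patient with a low pre-index sodium is counted as label-adherent. Those with E87.1 or another listed contraindication are not.
- A reader might infer that history of hyponatraemia rests on E87.1 throughout. SAP Table 73 points the covariate to a table with a biochemical definition.
- A reader might infer a large bias. An overstatement of 82% can be produced (p = 10%, s = 10%, RR = 10: f = 0.09/0.99 = 9.1%, times 9), but it needs three extremes at once and ignores overlap.
- A reader might infer that the contrast between the two label groups must shrink. Reclassified patients may also lower the rate in the contraindicated group, so this is not assured.

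**Conclusion.** The point holds for the Danish label-status analysis, limited to patients in the four covered regions with a recorded pre-index sodium <130 mmol/L, no E87.1 code and no other listed contraindication. The misplacement follows from the definitions as written. That it overstates the label-adherent rate depends on these patients having a higher later event rate, which section 7 supports. The size is not known: about 7 to 64 of roughly 1413 patients and 0.5% to 41% rest wholly on the assumed ranges, before overlap. The reach is mainly one Denmark-only secondary table in a descriptive study. This is a worthwhile, cheap improvement to that analysis, not a demonstrated large bias.

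**What to change.** For Danish patients in the four covered regions, add to SAP Table 71 and the objective 9 text a derived variable: E87.1 or any recorded serum sodium <130 mmol/L dated before index. The cut-off is the study's own for clinically significant hyponatraemia. It serves here as an analytic definition only and says nothing about who should be treated.

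- Report Table 40 and the other Danish label-status results with this variable beside the E87.1-only version.
- State how many patients it reclassifies and how many had any pre-index sodium test.
- Keep E87.1 alone for cross-country and pooled results.
- Reconcile the definitions of history: protocol Table A2 and SAP Table 71 against protocol Table A4 (which points to the LUTS drug codes) and SAP Table 73 (which points to the <135 mmol/L definition in Table 72).
- Reconcile protocol section 9.4.1.4 and SAP section 6.1.4 with the sodium covariate in section 9.3.3, so that it is clear that pre-index sodium is extracted.

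The cost is SAP wording, one derived variable from a database already linked for outcomes, and a second column of Danish results. The downsides are that Denmark carries two definitions and that the laboratory-based one depends on prior testing.
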